7.4. Follow-up Period

For each clinic visit there is a required timeline for the visit, as shown in the Time & Events Table. For each of these visits, the data described in Table 8 must be collected.

	Enrollment			Foll	Follow-up		
	FU 1:	FU2:	FU3:	FU4:	FU5:	FU6:	
Event/Visit	Pre-Op	Surgery	1 week	6 weeks	12 weeks	24 weeks	
	-90 to 0		1 to 14				
	days from		days				
	day of		after	±2			
Required Timing	surgery	0	surgery	weeks	±2 weeks	±4 weeks	
The signing of the informed							
consent form	Х						
Inclusion/Exclusion criteria	Х						
Demographic data and medical							
history enquiry	Х						
Concise patient self-rated health							
measurement scale (SF-12v2)	Х				Х	Х	
EQ5D	Х				Х	Х	
Harris Hip Score					Х	Х	
Subject history	Х						
Urine pregnancy test ¹	Х						
Frontal and lateral X-ray of							
fracture sites	Х		Х	х	х	х	
Surgical reduction and							
intramedullary nail fixation		х					
Surgeon's evaluation on product							
operability during operation		х					
Wound healing assessment ²			Х				
Local physical examination	Х		Х	Х	Х	Х	
Concomitant drugs ³	Х	Х	Х	Х	Х	Х	
Adverse event		X4	Х	Х	Х	Х	
Serious adverse event		X4	Х	Х	Х	Х	
Blood chemistry	Х	X ⁵					

1. Urine pregnancy tests: women of childbearing age only.

2. Wound healing condition is assessed until wound healing.

3. Concomitant Drug Table should include only pain killers and anti-osteoporosis drugs.

4. Adverse events and serious adverse events should be recorded starting at the time of patient randomization.

5. Second Laboratory Test analyses performed during post-op recovery phase per site standard of care. The results closer to the time of surgery will be recorded.

Unscheduled Visits

If in between protocol required visits/telephone contacts, the site study team learns of any interventional treatment that a subject has undergone or study-related reportable adverse events, as defined in Section 8.0, the relevant information will be captured on the appropriate CRFs. All diagnostic radiographic films will be reviewed by the independent radiographic reviewer. All relevant source documentation required to assess the event will be maintained in the subject files and all relevant documentation required for event adjudication will be provided as requested by the Sponsor.

Clinical follow-up

The Investigator will be required to document clinical assessment in the medical and research source documents.

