6.4 Detailed rules for determination of analysis population set and flow chart

- (1) No investigational device is implanted: Subjects obtain random numbers but do not use any study-related treatment (implantation study group, control group or third party products);
- (2) Violation of inclusion and exclusion criteria: The subjects do not meet the inclusion criteria or meet the exclusion criteria set in the study protocol, and the violation of this protocol will seriously affect the results of primary efficacy endpoints; the sponsor, investigators and statisticians will jointly determine through a blind review meeting whether the protocol violation will seriously affect the results of primary efficacy endpoints;
- (3) Loss to follow-up during the trial: Subjects are unable to obtain the fracture union rate 24 weeks after the primary endpoint surgery;
- (4) Cross enrollment: Subjects randomly assigned to the study group receive the control products, while subjects randomly assigned to the control group receive the investigational products;
- (5) Out-of-window time: The difference between the follow-up date at 24 weeks after primary endpoint surgery and the surgery date do not fall within the range of [140, 196], and the violation of this protocol may seriously affect the results of primary efficacy endpoints; the sponsor, investigators and statisticians will jointly determine through a blind review meeting whether the protocol violation will seriously affect the results of primary efficacy endpoints;
- (6) Out-of-specification use of investigational products: The specifications of the device implanted in the subject are not within the specification range specified in the study protocol;
- (7) Use of third party products: The subjects randomly assigned to the study group or the control group use third party products;

(8) FAS = Number of subjects enrolled in the trial - Number of subjects not implanted with any investigational device;

PPS = FAS - Number of subjects who seriously violate the study protocol;

ATS = PPS + Number of cross-enrolled subjects alone; ATS will be displayed if subjects are cross-enrolled in the trial, while ATS will not be displayed if no cross-enrollment occurs.

Number of subjects who seriously violate the study protocol = Violation of inclusion and exclusion criteria + Loss to follow-up during the trial + Cross enrollment + Out-of-window time + Out-of-specification use of investigational products + Use of third party products;

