6.5 Missing values, abnormal values and outlying values

For possible missing data in the study process, the missing of primary efficacy endpoints will be carried forward only in principle during the analysis. LOCF (Last Observation Carry Forward) was used as sensitivity analysis for the missing of primary efficacy endpoints. That is, the last observed value is used to replace the missing value. In the sensitivity analysis of the LOCF, the last observed value is "Nonunion of fracture " unless the fracture union is definitive. Other missing indicators will not be carried forward and will be directly analyzed based on the actually observed data. Error and unreasonable data will be processed in the data cleaning process before statistical analysis. For withdrawal of subjects, this part of patient information will still be included in the final statistical analysis. Specific reasons for discontinuation or withdrawal of all patients will be explained in detail in the statistical report, and the missing primary endpoint due to early withdrawal will be analyzed according to the above strategy for processing missing values.

If the date (MMDDYYYY) of collection (non-CEC review data) during the trial is filled in with "UK" or "NA", no treatment will be done.

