7.3 Primary endpoint

The primary endpoint is the fracture union rate 24 weeks after surgery.

Fracture union success is a composite endpoint; in order for an individual subject's surgery implanted with TFNA or PFNA-II to be considered successful he/she must satisfy all of the following criteria:

- 1. No focal tenderness or lengthwise percussion pain, or abnormal movement
- 2. The frontal/lateral X-ray examination shows the vague or no fracture gap, or the continuous callus passing across the fracture line
- 3. No deformation or breakage is found in the investigational product

Calculation principle: Based on the postoperative 24-week follow-up of the fracture status and the X-ray examination results of the fracture site, the calculation principle is as follows:

- 1. It is determined as 'Yes' when the focal tenderness, lengthwise percussion pain and abnormal activity at the postoperative 24-week follow-up of the fracture are filled as 'NA', 'NA' and 'No', respectively;
- 2. It is determined as 'Yes' when the X-ray examination at the fracture site 24 weeks after surgery shows that the fracture line is 'vague' or 'disappeared'; or that the frontal/lateral X-ray examination shows the continuous callus passing across the fracture line is filled as 'Yes';
- ③. It is determined as 'Yes' when the X-ray examination at the fracture site 24 weeks after surgery shows that the implant is filled as 'good';

If (1), (2) and (3) are determined as 'Yes', then the successful fracture union 24 weeks after surgery is determined as 'Yes'; if one of them is missing, it is determined as missing, that is, 'loss to follow-up during the trial'; others are determined as 'No';

For the primary endpoint, the analysis bases on the actual data (except missing data). LOCF (Last Observation Carry Forward) was used as sensitivity analysis for the missing of primary efficacy endpoints. The below 2 analysis tests will be used for the above analysis, and estimates of the differences in efficacy between the groups and bilateral two-sided 95% confidence interval will be given:

(1) CMH chi-square test with adjusted central effects;

Calculation method for non – inferiority P value:

Se=(Rate difference 95% upper limit of confidence interval - Rate difference 95% low limit of confidence interval)/2/ probit (1-0.05/2);

Z=(Investigational group-control group of difference in fracture union rates- non-inferiority margin)/Se;

P value=1-probnorm(Z);

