2. The likelihood ratio Chi-square test or Fisher's exact probability test is used to analyze the intergroup comparison of qualitative indicators;

			-	
Indicator	Study group	Control group	Statistics	P value
Successful fracture union 24 weeks at	ter surgery ^{#1}			
Number of subjects (N miss)	XXX (XXX)	XXX (XXX)	X.XXXX	X.XXXX
Yes	XXX (XX.X%)	XXX (XX.X%)		
No	XXX (XX.X%)	XXX (XX.X%)		
Difference in success rate (study group - c	ontrol group) and 95% CI	XX.X% [XX.X	%; XX.X%]	
P value in non-inferiori	e 1/	X.XXXX		
Difference in success rate (study group - c	ontrol group) and 95% CI	XX.X% [XX.X	%; XX.X%]	
P value in non-inferiori	ty test #4	X.XXXX		
Successful fracture union 24 weeks at	ter surgery ^{#2}			
Number of subjects (N miss)	XXX (XXX)	XXX (XXX)		
Yes	XXX (XX.X%)	XXX		
		(XX.X%)		
No	XXX (XX.X%)	XXX		
		(XX.X%)		
Difference in success rate (study group - c	ontrol group) and 95% CI	XX.X% [XX.X	%; XX.X%]	
P value in non-inferiori	ty test #3	X.XXXX		
Difference in success rate (study group - c	• •	XX.X% [XX.X	%; XX.X%]	
P value in non-inferiori	ty test #4	X.XXXX		

Table 30 (FAS) Primary endpoint - Statistical analysis results of subjects'fracture union rate 24 weeks after surgery

Notes: 1. #3 is analyzed by CMH chi-square test with adjusted sites, estimate the difference in success rate and non-inferiority test the P value;

#4 is analyzed by Continuous correction Newcombe-Wilson for non-adjusted central, estimate the difference in success rate and non-inferiority test the P value;

2. #1: The primary efficacy indicators of the subjects lost to follow-up during the trial were not processed;

#2: The primary efficacy indicators of the subjects lost to follow-up during the trial were carried forward by LOCF;

3. If the lower limit of 95% CI of the difference in the rates of the study group and the control group is greater than the non-inferiority margin of -10%, then the investigational product is considered non-inferior to the control product, i.e., the non-inferiority conclusion is established in this trial.

Indicator	Study group	Control group	Statistics	P value
Site 01 Beijing Jishuitan Hospital - Su	accessful fracture unio	on 24 weeks after su	rgery	
Number of subjects (N miss)	XXX (XXX)	XXX (XXX)	X.XXXX	X.XXXX
Yes	XXX (XX.X%)	XXX (XX.X%)		
No	XXX (XX.X%)	XXX (XX.X%)		
Site 02 Peking University Third Hosp	ital - Successful fract	ure union 24 weeks	after surgery	
Number of subjects (N miss)	XXX (XXX)	XXX (XXX)	X.XXXX	X.XXXX

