Number of subjects (N miss)	XXX (XXX)	XXX (XXX)	X.XXXX	X.XXXX
Yes	XXX (XX.X%)	XXX (XX.X%)		
No	XXX (XX.X%)	XXX (XX.X%)		

Notes: 1. #1: hospital XXX, hospital XXX and hospital XXX merged;

2. The likelihood ratio Chi-square test or Fisher's exact probability test is used to analyze the intergroup comparison of qualitative indicators;

Table 32 (PPS) Primary endpoint - Statistical analysis results of subjects'fracture union rate 24 weeks after surgery

Indicator	Study group	Control group	Statistics	P value
Successful fracture union 24 weeks a	fter surgery			
Number of subjects (N miss)	XXX (XXX)	XXX (XXX)	X.XXXX	X.XXXX
Yes	XXX (XX.X%)	XXX (XX.X%)		
No	XXX (XX.X%)	XXX (XX.X%)		
Difference in success rate (study group - c	control group) and 95% (CI XX.X% [XX.X	[%; XX.X%]	
P value in non-inferiori	ity test #1	X.XXXX		
Difference in success rate (study group - c	control group) and 95% (CI XX.X% [XX.X	X%; XX.X%]	
P value in non-inferior	ity test #2	X.XXXX		

Notes: 1. #1 is analyzed by CMH chi-square test with adjusted sites, estimate the difference in success rate and non-inferiority test the P value;

#2 is analyzed by Continuous correction Newcombe-Wilson for non-adjusted central, estimate the difference in success rate and non-inferiority test the P value;

2. If the lower limit of 95% CI of the difference in the rates of the study group and the control group is greater than the non-inferiority margin of -10%, then the investigational product is considered non-inferior to the control product, i.e., the non-inferiority conclusion is established in this trial.

Table 33 (ATS) Primary endpoint - Statistical analysis results of subjects'fracture union rate 24 weeks after surgery

Indicator	Study group	Control group	Statistics	P value
Successful fracture union 24 weeks a	ifter surgery			
Number of subjects (N miss)	XXX (XXX)	XXX (XXX)	X.XXXX	X.XXXX
Yes	XXX (XX.X%)	XXX (XX.X%)		
No	XXX (XX.X%)	XXX (XX.X%)		
Difference in success rate (study group - P value in non-inferior		CI XX.X% [XX.X X.XXXX	X%; XX.X%]	
Difference in success rate (study group - P value in non-inferior		CI XX.X% [XX.X X.XXXX	X%; XX.X%]	

Notes: 1. #1 is analyzed by CMH chi-square test with adjusted sites, estimate the difference in success rate and non-inferiority test the P value;

#2 is analyzed by Continuous correction Newcombe-Wilson for non-adjusted central, estimate the difference in success rate and non-inferiority test the P value;

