Number of subjects (N miss)	XXX (XXX)	XXX (XXX)	X.XXXX	X.XXXX
Yes	XXX (XX.X%)	XXX (XX.X%)		
No	XXX (XX.X%)	XXX (XX.X%)		

Notes: 1. The likelihood ratio Chi-square test or Fisher's exact probability test is used to analyze the intergroup comparison of qualitative indicators;

Indicator	Study group	Control group	Statistics	P value
Wound healing - healing grade				
Number of subjects (N miss)	XXX (XXX)	XXX (XXX)	X.XXXX	X.XXXX
А	XXX (XX.X%)	XXX (XX.X%)		
В	XXX (XX.X%)	XXX (XX.X%)		
С	XXX (XX.X%)	XXX (XX.X%)		
Wound healing - incision category				
Number of subjects (N miss)	XXX (XXX)	XXX (XXX)	X.XXXX	X.XXXX
Class I	XXX (XX.X%)	XXX (XX.X%)		
Class II	XXX (XX.X%)	XXX (XX.X%)		
Physical sign - Focal tenderness				
Number of subjects (N miss)	XXX (XXX)	XXX (XXX)	X.XXXX	X.XXXX
NA	XXX (XX.X%)	XXX (XX.X%)		
Mild	XXX (XX.X%)	XXX (XX.X%)		
Severe	XXX (XX.X%)	XXX (XX.X%)		
Physical sign - Lengthwise percussio	n pain			
Number of subjects (N miss)	XXX (XXX)	XXX (XXX)	X.XXXX	X.XXXX
NA	XXX (XX.X%)	XXX (XX.X%)		
Mild	XXX (XX.X%)	XXX (XX.X%)		
Severe	XXX (XX.X%)	XXX (XX.X%)		
Physical sign - Abnormal activity				
Number of subjects (N miss)	XXX (XXX)	XXX (XXX)	X.XXXX	X.XXXX
Yes	XXX (XX.X%)	XXX (XX.X%)		
No	XXX (XX.X%)	XXX (XX.X%)		
Evaluate postoperative weight-bearing	ıg			
Number of subjects (N miss)	XXX (XXX)	XXX (XXX) XXX	X.XXXX	X.XXXX
No weight-bearing	XXX (XX.X%)	(XX.X%)		
Lower degree of weight-bearing (support with two crutches) Higher degree of weight-	XXX (XX.X%)	XXX (XX.X%)		
bearing (support with one crutch)	XXX (XX.X%)	XXX (XX.X%)		
Fully weight-bearing (support without crutch)	XXX (XX.X%)	XXX (XX.X%)		

Table 72Statistical analysis results of subjects' fractures 24 weeks after
surgery

After the investigational device is implanted, whether external fixation is required to enhance the

Medical Research & Biometrics Center, National	Version No.: V1.0	130/129
Center for Cardiovascular Diseases		

stability of the fracture site				
Number of subjects (N miss)	XXX (XXX)	XXX (XXX)	X.XXXX	X.XXXX
Yes	XXX (XX.X%)	XXX		
		(XX.X%)		
No	XXX (XX.X%)	XXX		
		(XX.X%)		

Notes: 1. The likelihood ratio Chi-square test or Fisher's exact probability test is used to analyze the intergroup comparison of qualitative indicators;

2. Investigational device: Trochanteric Fixation Nail Advanced (TFNA); control device: Proximal Femoral Nail Antirotation (PFNA-II);

Indicator	Study group	Control group	Statistics	P value
Reduction				

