Number of subjects (N miss)	XXX (XXX)	XXX (XXX)	X.XXXX	X.XXXX
Stable	XXX (XX.X%)	XXX (XX.X%)		
Loss of reduction	XXX (XX.X%)	XXX (XX.X%)		
Is the re-operation required				
Number of subjects (N miss)	XXX (XXX)	XXX (XXX)	X.XXXX	X.XXXX
Yes	XXX (XX.X%)	XXX (XX.X%)		
No	XXX (XX.X%)	XXX (XX.X%)		
Implant				
Number of subjects (N miss)	XXX (XXX)	XXX (XXX)	X.XXXX	X.XXXX
Good	XXX (XX.X%)	XXX (XX.X%)		
Rupture of screw/bolt	XXX (XX.X%)	XXX (XX.X%)		
Rupture of intramedullary nail	XXX (XX.X%)	XXX (XX.X%)		
Displacement of screw/bolt	XXX (XX.X%)	XXX (XX.X%)		
Displacement of intramedullary nail	XXX (XX.X%)	XXX (XX.X%)		
Fracture line	VVV (VVV)	VVV (VVV)	V VVVV	v vvvv
Number of subjects (N miss)	XXX (XXX)	XXX (XXX)	X.XXXX	X.XXXX
Clear	XXX (XX.X%)	XXX (XX.X%)		
Vague	$\begin{array}{c} XXX (XX.X\%) \\ XXX (XX V\%) \end{array}$	$\begin{array}{c} XXX (XX.X\%) \\ XXX (XX Y\%) \end{array}$		
Disappeared Callus	XXX (XX.X%)	XXX (XX.X%)		
	VVV (VVV)	VVV (VVV)	X.XXXX	X.XXXX
Number of subjects (N miss) NA	XXX (XXX)	XXX (XXX)	Λ.ΛΛΛΛ	Λ.ΛΛΛΛ
Intermittent	XXX (XX.X%)	$\begin{array}{c} XXX (XX.X\%) \\ YYY (YY Y\%) \end{array}$		
Continuous	XXX (XX.X%) XXX (XX.X%)	XXX (XX.X%) XXX (XX.X%)		
The frontal/lateral X-ray examination	· · · · ·	· · · · ·	and the free stur	lina
Number of subjects (N miss)		XXX (XXX)	X.XXXX	X.XXXX
Yes	XXX (XXX) XXX (XX.X%)	$\begin{array}{c} \text{XXX} (\text{XX.X\%}) \\ \text{XXX} (\text{XX.X\%}) \end{array}$	Λ.ΛΛΛΛ	Λ.ΛΛΛΛ
No		· · · · ·		
	XXX (XX.X%)	XXX (XX.X%)		
Determine the fracture union condition		VVV (VVV)	v vvvv	V VVVV
Number of subjects (N miss)	$\begin{array}{c} XXX (XXX) \\ YYY (YY Y0) \end{array}$	XXX (XXX)	X.XXXX	X.XXXX
No union	XXX (XX.X%)	$\begin{array}{c} XXX (XX.X\%) \\ YYY (YY Y\%) \end{array}$		
Union	XXX (XX.X%)	XXX (XX.X%)		

Table 73Statistical analysis results of subjects' x-ray examination at the
fracture site 24 weeks after surgery

Notes: 1. The likelihood ratio Chi-square test or Fisher's exact probability test is used to analyze the intergroup comparison of qualitative indicators;

2. Investigational device: Trochanteric Fixation Nail Advanced (TFNA); control device: Proximal Femoral Nail Antirotation (PFNA-II);

T 1' /				
Indicator	Study group	Control group	Statistics	P value
White blood cell (WBC)				
Number of subjects (N miss)	XXX (XXX)	XXX (XXX)	X.XXXX	X.XXXX
Normal \rightarrow Abnormal (with clinical significance)	XXX (XX.X%)	XXX (XX.X%)		
Normal \rightarrow Abnormal (without clinical significance)	XXX (XX.X%)	XXX (XX.X%)		

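### SAP 7.3 codes the primary composite as missing when any component is missing, even if another component has already failed at week 24

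*SAP*

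**What the plan says.** SAP 7.3 defines success as meeting all three criteria: no tenderness, percussion pain or abnormal movement; radiographic union; and an intact implant. It then gives three branches in order:

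- *Yes* if all three components are *Yes*.
- Missing for incomplete data: "if one of them is missing, it is determined as missing, that is", loss to follow-up during the trial.
- *No* for all others.

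There is no exception for a component already observed to fail.

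The consequences are set elsewhere in the SAP:

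- **Main FAS result.** Table 30, note #1: "The primary efficacy indicators of the subjects lost to follow-up during the trial were not processed".
- **PPS.** SAP 6.4(3) defines loss to follow-up as "Subjects are unable to obtain the fracture union rate 24 weeks after the primary endpoint surgery". It counts as a serious violation, and serious violations are subtracted from the FAS to form the PPS. The ATS adds back only subjects whose sole violation is cross-enrolment.
- **LOCF.** SAP 6.5 sets the carried-forward value to nonunion "unless the fracture union is definitive". This is a sensitivity analysis, shown as a second block in Table 30 (FAS). Tables 32 (PPS) and 33 (ATS) have no such block.

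The components come from two sources. Examination items such as "Physical sign - Focal tenderness" are in Table 72. X-ray items such as "Rupture of intramedullary nail" are in Table 73. Each item has its own missing count. Protocol 7.4 schedules the X-ray and "Local physical examination" at the same visit, FU6.

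**The concern.** When success needs all of several criteria, one observed failure decides the outcome and the other components no longer matter. The SAP rule discards that information. It can discard only failures, because a subject with a missing component can never be a confirmed success.

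Removing failures raises the observed union rate in whichever arm loses them. If failures are lost at the same rate in both arms and TFNA is truly worse, the observed difference shrinks towards zero, which favours non-inferiority. Loss mainly from TFNA favours it more. Loss mainly from control works against it. The subjects concerned are dropped from every analysis that decides non-inferiority.

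**Working it through.** **1. Apply the rule.** Take a subject whose week-24 X-ray shows a ruptured nail and who has no tenderness entry. Component 3 is not *Yes*, so the first branch fails. Component 1 is missing, so the second branch applies and the composite is missing. The third branch is never reached. Neither document makes an exception.

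**2. The plan's own figures (SAP 6.2).** Inputs: union 95% in both arms, margin 0.10, one-sided alpha 0.025, power 80%, attrition 20%.

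n = (1.960 + 0.842)² × 2 × 0.95 × 0.05 / 0.10² = 74.6, so 75 per arm. 75 / 0.80 = 93.75, so 94 per arm. Both reproduce. At 5% failure, 94 per arm gives about 5 failures and 75 per arm about 4.

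**3. Effect of one dropped TFNA failure.** The lower limit for d = TFNA minus control must exceed -10%.

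- Wald: d − 1.96 × √(p₁q₁/n₁ + p₂q₂/n₂), with q = 1 − p.
- Newcombe-Wilson with continuity correction (SAP test 2): d − √((p₁ − l₁)² + (u₂ − p₂)²), where l and u are the continuity-corrected Wilson limits of each arm.

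Worked case, 89/94 in both arms (p = 0.9468):

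- Wald: −1.96 × √(2 × 0.9468 × 0.0532 / 94) = −6.42%.
- Newcombe: l = 0.8745, u = 0.9803, so −√(0.0723² + 0.0334²) = −7.96%.
- After dropping one TFNA failure (89/93): d = +1.02 points, and Wald = 1.02 − 6.13 = −5.11%.

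| TFNA, failure kept → dropped | Control | Wald | Newcombe cc |
|---|---|---|---|
| 89/94 → 89/93 | 89/94 | −6.42 → −5.11 | −7.96 → −6.71 |
| 87/94 → 87/93 | 89/94 | −9.11 → −7.88 | **−10.61 → −9.44** |
| 86/94 → 86/93 | 89/94 | **−10.43 → −9.23** | −11.90 → −10.76 |
| 71/75 → 71/74 | 71/75 | −7.19 → −5.51 | −9.21 → −7.61 |
| 71/76 → 71/75 | 71/75 | −8.79 → −7.19 | **−10.72 → −9.21** |

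Bold marks a change of verdict. The planned cases (rows 1 and 4) do not change.

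**4. How often a trial lies that close to the margin.** With true union 95% in both arms and 94 per arm, exact binomial enumeration gives the probability that dropping one TFNA failure turns a fail into a pass: 3.8% (Wald) and 10.5% (Newcombe cc). Simulation of a site-adjusted analysis gives about 5.4%. All three are conditional on such a subject existing.

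**5. False non-inferiority at the margin.** True rates are 95% control and 85% TFNA. Each failure is lost with probability f, leaving numerator and denominator. The apparent deficit is 0.95/(1 − 0.05f) − 0.85/(1 − 0.15f), that is 10.0, 9.6 and 9.2 points at f = 0, 5% and 10%.

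| Loss in both arms | f = 0 | 5% | 10% |
|---|---|---|---|
| 94 per arm, Wald | 3.3% | 4.1% | 5.2% |
| 94 per arm, site-adjusted | 3.3% | 4.1% | 5.2% |
| 94 per arm, Newcombe cc | 1.6% | 1.9% | 2.4% |
| 75 per arm, Wald | 3.7% | 4.5% | 5.5% |
| 75 per arm, Newcombe cc | 1.5% | 1.8% | 2.2% |

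With f = 10% in one arm only (94 per arm), Wald / Newcombe cc give 6.2% / 3.1% for TFNA failures and 2.7% / 1.2% for control failures.

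The site-adjusted row is a Mantel-Haenszel risk difference with Sato variance, simulated over the 10 sites of SAP Tables 4–13. It assumes 9–10 subjects per arm per site and has Monte Carlo error up to 0.06 points.

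**6. What f means in subjects.** 94 × 0.05 × f = 0.2 to 0.5 per arm at the planned failure rate for f = 5–10%. In TFNA at 15% failure, 94 × 0.15 × f = 0.7 to 1.4.

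**The case against.** The strongest reply is that the pattern will rarely occur. Components 2 and 3 come from the same X-ray, and the examination is due at the same visit within ±4 weeks. Protocol 10.10.3 sends missing items back to the site as queries. For the rule to bite, one item must stay missing after query while another has failed. Separate missing counts in table shells show only that this is possible. The documents give no value for f, the planned result passes either way, and under equal loss the Newcombe error stays below 2.5% at every f shown. All of this stands and limits the size of the point.

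The information is also not hidden. Table 73 reports implant rupture by arm, and Protocol 10.10.5 compares the radiographic and breakage components separately. LOCF on the FAS should return most such subjects as nonunion. That recovery is not assured: union is recorded at week 12 (Table 68), and the SAP does not say whether an earlier definitive union would be carried forward over a failed week-24 component. It is also confined to a sensitivity row.

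Finally, SAP 6.4(3) and Protocol 10.10.5 turn on whether the outcome is obtainable or known, and an observed failure arguably is. But SAP 7.3 is the operative derivation, and it equates any missing component with loss to follow-up. The tension is a reason to correct 7.3, not evidence that the rule is harmless.

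**Conclusion.** The concern holds. As written, SAP 7.3 turns a determined failure of the primary endpoint into a missing value and removes it from the main FAS estimate, the PPS and the ATS.

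The expected effect is small. One dropped TFNA failure moves the lower limit by about 1.2 to 1.7 points and changes the verdict only near the margin. The error-rate increase of 0.8 to 1.9 points (Wald, 94 per arm) rests on an assumed f of 5–10%, equal loss in both arms, and a true difference exactly at the margin. The excess over 2.5% already present at f = 0 (Wald and site-adjusted) has nothing to do with missing data. Direction depends on which arm loses failures.

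It should be fixed because the rule is logically wrong on the primary endpoint of a registration trial, and a correction made after the data are seen would look post hoc.

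**What to change.** In SAP 7.3, order the branches as follows:

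- *No* if any observed component fails.
- *Yes* if all three are *Yes*.
- Missing only if no observed component has failed and at least one is missing.

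Apply this before classifying loss to follow-up under SAP 6.4(3). A subject coded *No* then has a known result, so neither that exclusion nor LOCF applies. Return to the PPS still depends on the other exclusions. Protocol 10.8 lists non-compliance with procedures as a major deviation, while Appendix A classes incomplete testing as minor, so state which applies to a single missing week-24 item.

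The cost is one clause and the matching derivation code: no new data, no change in sample size, and no protocol amendment, since Protocol 10.10.5 already analyses per-protocol patients whose outcome is known.

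Separately, and of less weight, Protocol 8.5, 9.1 and 9.2 and SAP 7.3 should be reconciled on how a subject revised before week 24 is followed and scored.
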